5. OBJECTIVES

5.1. Primary Objectives

- To evaluate PV and ISV using the FAST PV Technology and iohexol in patients on chronic dialysis predialysis.
- To evaluate the interaction between PV and ISV measured after a dialysis with a repeat injection of VFI using the FAST PV Technology.
- To assess the safety and tolerability of visible fluorescent injectate (VFI) (employing the FAST PV Technology) in chronic dialysis patients with extremely reduced or no renal function.

6. STUDY DESIGN

6.1. Study Design and Overview

This is a pilot, single site, open-label study designed to evaluate the safety, tolerability, and performance of the FAST PV Technology in dialysis patients.

The planned dose cohorts are presented in [Table 3](#).

Cohort	Population	eGFR ^a	Base VFI Dose ^b	Number of Doses	Comparator Dose	Number of Doses	Number of Subjects
1	Dialysis Subjects	≤ 2 mL/min/1.73m ²	3 mL	2	Iohexol 5 mL	2	Up to 10

Abbreviation: N/A = not applicable

^a. Patients must be on chronic hemodialysis for ≥ 3 months and oliguric defined as ≤ 2 urinary voids per day.

^b. 3 mL for subjects/patients ≥ 40 and ≤ 100 kg + 1 mL for every 40 kg increase in body weight

Administration of VFI will occur within 28 days of screening.

Patients will receive 1 dose of VFI and 1 dose of iohexol approximately 4 hours prior to undergoing dialysis followed by a second dose of VFI and iohexol approximately 1 hour after completing dialysis. Patients will be discharged following completion of Day 1 activities. Patients will be seen and evaluated on their next 2 dialysis sessions for any adverse reaction by answering questions about their health, approximately on Day 3 and Day 8. A follow-up phone call will be performed on Day 31 (± 1 day).

Refer to [Table 1](#) for the Schedules of Assessments and Procedures.

6.1.1. Duration of Study

Participation is expected to last up to 59 days, including a screening period of up to 28 days and an on-study period of up to 31 days (consisting of a single performance period and a follow-up phone call).

6.1.2. Definition of Study Completion

Discharge/EOS procedures will be performed as specified in the Schedules of Assessments and Procedures ([Table 1](#)); subjects/patients who terminate from the study early will have discharge/EOS procedures performed at the time of discontinuation. Subjects/patients with ongoing clinically significant clinical or laboratory findings will be followed until the finding is resolved or medically stable; reasonable attempts will be made to follow-up with subjects/patients. The subject's/patient's participation in the study will end once all study assessments and follow-up have been completed.

6.1.3. End of Study

The end of the study is defined as the date when the last subject/patient has completed all study procedures up to and including the follow-up phone call/EOS visit as outlined in the Schedules of Assessments and Procedures ([Table 1](#)).

7. SELECTION AND WITHDRAWAL OF SUBJECTS

Subjects/patients must meet all the following criteria in order to be enrolled in the study.

7.1. Inclusion Criteria

Subjects/patients must meet all inclusion criteria to be eligible for study participation.

1. Males or females ≥ 18 years of age.
2. Females must be of non-childbearing potential (eg, postmenopausal [defined cessation of regular menstrual periods for at least 1 year confirmed by age ≥ 60 or surgically sterile by hysterectomy, bilateral oophorectomy, or bilateral tubal ligation [documentation required]]) or be using a medically acceptable form of birth control (a barrier method, intrauterine device, or hormonal contraception) from screening through 30 days after administration of the last dose of VFI.
3. Males who are sexually active and whose partners are females of childbearing potential must agree to practice abstinence or use condoms from screening through 90 days after administration of the last dose of VFI, and their partners must be willing to use a medically acceptable method of contraception (a barrier method, intrauterine device, or hormonal contraception) from screening through 90 days after administration of the last dose of VFI.
4. Males must agree to not donate sperm from screening through 90 days after administration of the last dose of VFI.
5. Subjects/patients must be able to communicate effectively with the study personnel.
6. Patients must be on chronic hemodialysis for ≥ 3 months and oliguric defined as ≤ 2 urinary voids per day.
7. Patients must have an average interdialytic weight gain of at least 2 kg.
8. Patients must have an A-V dialysis shunt.
9. Patients must have a functioning A-V dialysis shunt, either fistula or graft.

7.2. Exclusion Criteria

Subjects/patients will not be eligible for study participation if they meet any of the exclusion criteria, or will be discontinued at the discretion of the investigator if they develop any of the exclusion criteria during the study.

1. Subject is a pregnant or nursing (lactating) woman, where pregnancy is defined as the state of a female after conception and until the termination of gestation, confirmed by a positive human chorionic gonadotropin (hCG) laboratory test.
2. History or presence of conditions which, in the judgment of the investigator, are known to interfere with the distribution, metabolism, or excretion of drugs.
3. History or presence of conditions that may place the subject/patient at increased risk as determined by the investigator.

4. History of surgery or major trauma within 12 weeks of screening or surgery planned within 4 weeks of the study including during study participation.
5. Has taken other investigational drugs within 30 days or 5 half-lives of the investigational drug's PK, PD, or biological activity, whichever is longer, prior to first dose of VFI in this study.
6. Prior exposure to VFI or known allergy or hypersensitivity to dextran, 5-aminofluorescein dye, or 2-sulfohexamine rhodamine dye.
7. History of any clinically significant allergic or negative reactions, side effects, or anaphylaxis to iodine, dyes, shellfish, isotopes, or dextran molecules.
8. Significant blood loss (> 450 mL) or has donated 1 or more units of blood or plasma within 4 weeks prior to study participation.
9. Presence of significant hemodynamic instabilities defined as systolic BP <100 on dialysis requiring saline infusion in the past 4 weeks.
10. Presence of ascites and/or 4+ anasarca.
11. Any other condition or prior therapy that, in the investigator's opinion, would make the subject unsuitable for the study, or unable or unwilling to comply with the study procedures.
12. Involved in the planning or conduct of this study.
13. Unwilling or unlikely to comply with the requirements of the study.
14. Clinically significant ongoing bleeding, changing hemoglobin, or experienced significant blood loss within last 4 weeks.
15. Had a PRBC transfusion in the prior 2 weeks
16. Use of midodrine.
17. Any other condition or prior therapy that, in the investigator's opinion, is likely to deteriorate during study participation
18. Subjects suffering from significant non-cardiac diseases of other organ systems (eg, malignancies, significant neurological diseases).
19. Subject has a psychiatric disease or a history of illicit drug use that would prohibit them from complying with study requirements.
20. Use of hemodialysis catheter as primary vascular access for hemodialysis

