Statistical Analysis:	
Analysis Populations: Safety Population: All subjects who receive any amount of study product. Performance Population: All subjects who have either a PV or ISV measurement using any of the techniques under study.
 
Safety Analysis: The number and percentage of subjects reporting any treatment-emergent AE will be tabulated by system organ class, preferred term (coded using Medical Dictionary for Regulatory Activities), and cohort. Treatment-emergent AEs will be further classified by severity and relationship to study product. Vital signs and clinical laboratory test data (observed and change from baseline) will be summarized by cohort and time point using appropriate descriptive statistics. Physical examination findings results will only be listed.
 
Performance Analysis: PV and ISV Measurements determined by FAST PV Technology will be compared to measurements determined by iohexol for both Dose 1 and Dose 2. Basic statistical analyses including correlations and Bland-Altman plots will be performed. Changes in PV and ISV measurements between Dose 1 and Dose 2 determined by the FAST PV Technology and iohexol will be compared to the known volume of fluid removed during dialysis treatment. Basic statistical analyses including correlations and Bland-Altman plots will be performed. Residual amounts of FAST VFI will be assayed on the Day 3 and Day 8 follow-up visits to assess the continued removal of the FAST VFI in this patient population.

Table 1. Schedule of Assessments and Procedures						
Study Procedure	Screening^a	Day 1		Follow-Up		Discharge^b
	Days -28 to -2	Dose 1	Dose 2	Day 3	Day 8	Day 31
Informed consent	X					
Inclusion/exclusion criteria ^a	X	X				
Demographics	X					
Height	X					
Body weight	X	X	X			
BMI ^c	X	X				
Medical and surgical history	X	X ^d				
Physical examination	X	X				
Vital signs ^e	X	X ^f	X ^f			
Clinical laboratory tests ^g		X ^{gh}	X ^h			
Hematocrit		X ⁱ	X ⁱ			
nT pro-BNP		X				
Creatinine phosphokinase		X ^h		X	X	
Liver function tests		X		X	X	
Timed Urine Collection ^j		X	X			
Pregnancy test (nonmenopausal females only)	X	X				
Outpatient visit	X	X	X	X	X	X
FAST VFI administration		X	X ^k			
Iohexol administration		X	X			
FD001 and FD003 plasma samples		Refer to Table 2		X ^l	X ^l	
Iohexol plasma samples		Refer to Table 2				
Adverse events		X	X	X	X	X
Serious adverse events		X	X	X	X	X
Concomitant medications	X	X	X			

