Abbreviations: BMI = body mass index; FD001 = 5 kD carboxymethyl dextran; FD003 = 150 kD carboxymethyl dextran; FSH = follicle-stimulating hormone; HBV = hepatitis B virus; HCV = hepatitis C virus; HIV = human immunodeficiency virus; VFI = visible fluorescent injectate.

^a. Assessments conducted upon enrollment will be used to reconfirm a subject's eligibility for enrollment into the study.

^b. Discharge procedures will be performed following completion of all Day 31 assessments. Subjects who terminate from the study early will have discharge procedures performed at the time of discontinuation.

^c. BMI will be calculated using the height obtained at screening.

^d. Medical and surgical history will be collected and documented to determine if any changes have occurred since screening.

^e. Vital signs will be measured after the subject has been resting quietly in a supine position or in the most recumbent position possible for at least 5 minutes.

^f. Vital signs will be measured within approximately 30 minutes prior to VFI and iohexol administrations and approximately 60-, 120- and 180-minutes post VFI and iohexol administrations.

^g. Refer to [Table 6](#) for a detailed list of clinical laboratory test parameters, which will be collected from the medical

Table 1. Schedule of Assessments and Procedures						
Study Procedure	Screening^a	Day 1		Follow-Up		Discharge^b
	Days -28 to -2	Dose 1	Dose 2	Day 3	Day 8	Day 31
record. h. BUN and serum creatinine will be drawn pre-dose dose 1 and post the dose 2 180 min VFI blood draw. i. Predose j. Pooled urine collection (from patient arrival to departure) to measure total volume, creatinine and urea nitrogen. No catheter. k. VFI administration of Dose 2 will occur approximately 8 hours following VFI administration of Dose 1 l. Blood samples to be drawn after dialysis session to allow for determination of any remaining FAST VFI. NOTE: In the event multiple postdose procedures are required to be conducted at the same nominal time point, the timing of performance blood sample collections will take priority over all other scheduled activities. In practice, the following order is recommended: (1) vital signs assessments; (2) performance blood sampling; (3) clinical laboratory tests sampling; (4) physical examination. Vital signs may be conducted up to 10 minutes prior to the nominal time to minimize the potential autonomic effects of blood draws on these measurements.						

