7.3. Subject Withdrawal

Subjects/patients are free to discontinue the study at any time, for any reason, and without prejudice to further treatment. The investigator may remove a subject/patient if, in the investigator's judgment, continued participation would pose unacceptable risk to the subject/patient or to the integrity of the study data. All procedures for early termination must be completed. Reasons for removal or withdrawal may include:

- Withdrawal of consent
- Administrative decision by the investigator or sponsor
- Ineligibility
- Significant protocol deviation
- Subject/patient noncompliance
- Safety concern by the investigator or sponsor
- Lost to follow-up

Subjects/patients who are withdrawn for reasons other than safety issues may be replaced at the discretion of the sponsor and investigator.

In the event of a subject's/patient's withdrawal, the investigator will promptly notify the sponsor and will make every effort to complete discharge procedures. All withdrawn subjects/patients with ongoing clinically significant clinical or laboratory findings will be followed until the finding is resolved or medically stable; reasonable attempts will be made to follow-up with subjects/patients.

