10.7. Drug-induced Liver Injury

Subjects will be monitored for signs of drug-induced liver injury (DILI). Study product will be withheld in the event of potential DILI.

Potential events of DILI will be defined as meeting all of the following criteria (as specified in the [FDA Guidance for Industry Drug-induced Liver Injury: Premarketing Clinical Evaluation, 2009](#)):

- Alanine aminotransferase or aspartate aminotransferase $> 3 \times$ ULN
- Total bilirubin $> 2 \times$ ULN without initial findings of cholestasis (elevated serum alkaline phosphatase)
- No other reason can be found to explain the combination of laboratory value increases (eg, acute viral hepatitis; alcoholic and autoimmune hepatitis; hepatobiliary disorders; nonalcoholic steatohepatitis; cardiovascular causes; concomitant treatments)

Potential events of DILI will be reported as SAEs ([Section 10.4](#)). All subjects with potential DILI will be closely followed until abnormalities return to normal or baseline or until all attempts to determine resolution of the event are exhausted.

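### A patient discontinued after receiving VFI is no longer required to have the Day 3 and Day 8 CPK, liver and residual-VFI draws

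*Protocol*

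**What the plan says.** All references are to the protocol.

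- **On-study use of the exclusions.** The opening of Section 7.2 states that patients "will be discontinued at the discretion of the investigator if they develop any of the exclusion criteria during the study". Criterion 9 reads "Presence of significant hemodynamic instabilities defined as systolic BP <100 on dialysis requiring saline infusion in the past 4 weeks".
- **Order on Day 1.** Sections 6.1 and 8.2 place Dose 1 about 4 hours before dialysis and Dose 2 about 1 hour after it.
- **Early termination.** Table 1 footnote b: "Subjects who terminate from the study early will have discharge procedures performed at the time of discontinuation". Section 6.1.2 repeats the rule: "subjects/patients who terminate from the study early will have discharge/EOS procedures performed at the time of discontinuation". Section 7.3 asks the investigator to try to complete the discharge procedures and adds: "All withdrawn subjects/patients with ongoing clinically significant clinical or laboratory findings will be followed until the finding is resolved or medically stable".
- **Schedule.** In Table 1, CPK and liver tests are marked under Dose 1, Day 3 and Day 8. FD001/FD003 samples follow Table 2 on Day 1 and are marked again on Day 3 and Day 8. The Discharge column is marked only for the visit, AEs and SAEs.
- **Purpose of the late samples.** The Synopsis says: "Residual amounts of FAST VFI will be assayed on the Day 3 and Day 8 follow-up visits to assess the continued removal".

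**The concern.** Discharge procedures carried out on Day 1 replace the later visits, and they contain no blood test. A patient who has received VFI and then leaves the study would have no required test that could show a later CPK or liver change, and no required check that VFI is being removed.

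Three statements in the protocol give those draws weight:

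- Section 11.3.1 makes clinical laboratory tests part of a primary safety endpoint.
- Section 4.6.2 says that VFI has not been given to dialysis patients before.
- Section 4.4.2.1 reports three CPK rises, all mild and judged possibly related, in the Phase 2b cohort with eGFR 15 to <30 mL/min/1.73 m².

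Visit schedules and procedures after discontinuation are set in the protocol. No analysis plan can recover blood that was not drawn.

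**Working it through.** The protocol has no figure of its own on this point: Section 11.1 describes about 10 subjects, not powered. The check is a trace through the text, followed by simple arithmetic for scale.

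**Trace for a patient removed after Dose 1 and before Dose 2**

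1. VFI has been given, so the patient is in the Safety Population (Section 11.2).
2. Systolic pressure below 100 needing saline in the Day 1 dialysis meets the wording of criterion 9. The Section 7.2 clause then permits discontinuation.
3. If the investigator discontinues the patient, footnote b and Section 6.1.2 apply the Discharge column at once: visit, AEs, SAEs.
4. Required draws that remain: CPK 0 of 2, liver tests 0 of 2, residual FD001/FD003 0 of 2. The Day 1 CPK entry carries footnote h, whose post-dose draw comes after the Dose 2 180-minute sample. This patient has no such sample.
5. Remaining follow-up: hypotension needing treatment is recorded as an AE (Section 9.5.3) and followed (Section 10), and significant findings already present are followed (Sections 6.1.2 and 7.3). None of these provisions requires a test for a change that has not yet been measured.

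Steps 3 and 5 apply equally to any other removal under Section 7.3 or 10.3, whatever its reason.

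**Size**

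- Planned values of each test on Day 3 and Day 8: 2 draws × 10 patients = 20. One patient removed: 2/20 = 10%.
- One-sided 95% upper bound on an event rate when none is seen in n patients: 1 − 0.05^(1/n).

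| Patients with follow-up draws | Upper bound |
|---|---|
| 10 | 1 − 0.05^(1/10) = 25.9% |
| 9 | 1 − 0.05^(1/9) = 28.3% |
| 8 | 1 − 0.05^(1/8) = 31.2% |

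Section 7.3 allows replacement only when the reason for withdrawal is not a safety issue. A removal for hypotension that is classed as a safety issue would therefore not be made up.

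**The case against.** The strongest objection is that the loss needs a chain of events: hypotension on dialysis, a choice to end participation instead of skipping Dose 2, no further test ordered, and then a silent laboratory change. Patients with such hypotension in the previous 4 weeks are excluded at entry. Sections 9.5.2, 9.5.3, 9.5.4, 10.1 and 10.7 treat stopping or withholding product separately from leaving the study, so the investigator can withhold Dose 2 and keep the patient on schedule. Section 10 also leaves room for extra tests. The study is an unpowered pilot with descriptive safety tables, and one patient moves the bound by only 2.4 percentage points (28.3 − 25.9). All of this stands and limits the weight of the point. It does not supply a rule that keeps the draws.

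Four stronger readings are tempting, but the documents do not support them:

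- **Every patient becomes ineligible after Dose 1.** Criterion 6 begins "Prior exposure to VFI or known allergy or hypersensitivity to dextran" and has no time limit. But the on-study clause concerns criteria that a patient develops, and Section 8.2 mandates a second dose for everyone. The criterion cannot sensibly mean the study's own Dose 1.
- **The rules contradict Section 10.7.** That section promises monitoring for liver injury but sets no schedule and does not say that monitoring continues after discontinuation. This is an omission, not a contradiction.
- **Slow FD003 clearance creates a special hazard.** Section 4.6.2 says FD003 exposure is unchanged from prior studies, and Section 4.4.2.2 reports it as independent of renal function. Section 4.6.2 also expects the first doses of VFI and iohexol to be removed at dialysis.
- **The Phase 2b CPK rises give a risk for dialysis patients.** Three of at most eight is at least 37.5%, but the exact 95% interval for 3/8 runs from 8.5% to 75.5% and the population differs. The events justify testing; they do not estimate a rate here.

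**Conclusion.** The point holds as an inexpensive improvement. Followed as written, footnote b and Sections 6.1.2 and 7.3 release a VFI-exposed patient who is discontinued from safety draws that are already scheduled. Intradialytic hypotension on Day 1 is a realistic route, but it is discretionary and not the only one.

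Per patient removed before Day 3, the loss is 10% of the planned Day 3 and Day 8 values of each test, and a zero-event bound of 28.3% in place of 25.9%. These figures assume 10 enrolled patients, one removed, no replacement and no draws taken voluntarily. The protocol gives no rate of such removals, and none is assumed. The patient stays in the Safety Population, and Dose 1 performance data already collected are kept, so the loss is confined to the later draws.

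A reader might infer that Section 7.2 forces removal or forbids later sampling. It does neither: removal is at the investigator's discretion, and the draws lapse only because nothing requires them.

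**What to change.** 1. **Essential.** In Table 1 footnote b, Section 6.1.2 and Section 7.3, state that any subject who has received VFI and whose Dose 2 is withheld, or who is discontinued, keeps the Day 3, Day 8 and Day 31 assessments in Table 1, unless consent is withdrawn or the subject is lost to follow-up. Changing Section 7.2 alone would not be enough, because removals under Sections 7.3 and 10.3 have the same effect.
2. **Supporting.** In Section 7.2, keep the on-study clause, since it gives useful stopping grounds such as pregnancy, new hypersensitivity and bleeding. Add that developing an exclusion criterion after Dose 1 leads first to withholding Dose 2, with safety follow-up continuing.
3. **Optional.** In criterion 6, limit prior VFI exposure to exposure before this study.

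The cost is a few sentences. No patients, visits or draws are added beyond Table 1, and footnote l already ties the residual-VFI samples to dialysis sessions. There are three downsides. The site follows a patient who is no longer receiving product. Residual-VFI values after one dose must be reported separately from those after two. For a patient who missed Dose 2, the Dose 1 to Dose 2 change in PV and ISV stays missing.

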7.3. Subject Withdrawal

Subjects/patients are free to discontinue the study at any time, for any reason, and without prejudice to further treatment. The investigator may remove a subject/patient if, in the investigator's judgment, continued participation would pose unacceptable risk to the subject/patient or to the integrity of the study data. All procedures for early termination must be completed. Reasons for removal or withdrawal may include:

- Withdrawal of consent
- Administrative decision by the investigator or sponsor
- Ineligibility
- Significant protocol deviation
- Subject/patient noncompliance
- Safety concern by the investigator or sponsor
- Lost to follow-up

Subjects/patients who are withdrawn for reasons other than safety issues may be replaced at the discretion of the sponsor and investigator.

In the event of a subject's/patient's withdrawal, the investigator will promptly notify the sponsor and will make every effort to complete discharge procedures. All withdrawn subjects/patients with ongoing clinically significant clinical or laboratory findings will be followed until the finding is resolved or medically stable; reasonable attempts will be made to follow-up with subjects/patients.

